12.1.3 Coding of Adverse Events

Adverse events will be coded using MedDRA, Version 22.0 or later.

12.1.4 Allocation of AEs to Treatment Periods

AEs will be allocated to treatment periods according to the time of onset of the adverse event (for handling of incomplete start dates, see section 19.3.5):

- *AE in Lead-in Study Period* – an AE that starts before first dose of IMP in study 16159B
- *AE in the Treatment Period* – an AE that starts at or after the date of first dose of IMP in study 16159B and at or before the date of the Primary Outcome/Withdrawal Visit
- *AE in the Safety Follow-up Period* – an AE that starts after the last visit in the Treatment Period

12.1.5 Presentation of Adverse Events

All adverse events will be listed for the APES, including a flag for TEAEs. A listing of all AEs occurring while on weekly dosing will also be presented.

An overview of the PYE, number and percentages of patients with TEAEs, serious adverse events (SAEs), TEAEs leading to withdrawal, and of patients who died will be provided based on the APTS. For TEAEs, SAEs, and adverse events leading to withdrawal, the total number of events will be included.

12.1.6 Presentation of Treatment-emergent Adverse Events

The following summaries will be provided for the APTS:

- TEAEs by SOC and preferred term
- TEAEs by preferred term – both by previous treatment and overall
- TEAEs occurring while on weekly dosing by preferred term
- TEAEs by sex and preferred term
- causally related TEAEs by SOC and preferred term
- TEAEs by intensity (*mild/moderate/severe*) and preferred term
- causally related TEAEs by intensity and preferred term
- TEAEs within the first 2 weeks of study 16159B by preferred term – both by previous treatment and overall

12.1.7 Presentation of Deaths

All adverse events for patients who died will be listed.

12.1.8 Presentation of Serious Adverse Events

All SAEs will be listed.

Treatment-emergent SAEs for the APTS will be summarized by:

- SOC and preferred term
- preferred term

Treatment-emergent SAEs for the APTS occurring while on weekly dosing will also be summarized by preferred term.

12.1.9 Presentation of Adverse Events Leading to Withdrawal

All adverse events leading to withdrawal will be listed.

TEAEs leading to withdrawal for the APTS will be summarized by:

- SOC and preferred term
- preferred term and previous treatment

Treatment-emergent AEs leading to the withdrawal occurring while on weekly dosing will also be summarized by preferred term for the APTS.

12.1.10 Adverse Events Leading to Dose Reduction

Adverse events leading to reduction of dose of Lu AF35700 in the Treatment Period will be listed.

Adverse events leading to reduction of dose of Lu AF35700 in the Treatment Period will be summarized by preferred term.

12.2 General Methodology for Other Safety Data

For details about data handling, see sections [19.1](#) and [19.2](#).

Unless otherwise specified, tables and graphs will be based on the APTS, and listings will be based on the APES.

All the tables and graphs will be presented for the total group.

The denominators for the summaries of a given variable will be based on the number of patients with non-missing values at a given visit or during the assessment period.

Descriptive statistics for the safety variables, both absolute values and changes from baseline, will be presented by visit and for the last assessment. All available post-baseline assessments will be included in the identification of the last assessment except for assessments made at the safety-follow-up visit.

The number and percentage of patients with at least one PCS value at any post-baseline assessment time point will be summarized by variable. All available assessments will be included in the evaluation of PCS values except for assessments made at the safety-follow-up visit.

For patients with post-baseline PCS values, listings will be provided including all available values for the variable, with flagging of PCS values and out-of-reference-range values.

All the adverse events in patients with post-baseline PCS values will be listed by previous treatment group and patient screening number (from the extension study); the listings will include all available values for the variable with flagging of PCS values and out-of-reference-range values, the assessment date, the change from baseline in PCS value, the preferred term for the adverse event, and start date, and stop date of the adverse event. The PCS values and adverse events will be listed in chronological order according to assessment date and the start date of the adverse event.

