### 17.3 Descriptive Statistics

In general, summary statistics (n, arithmetic mean, standard deviation, median, minimum and maximum values) will be presented for continuous variables and counts and, if relevant, percentages will be presented for categorical variables.

For patients coming from 16159A, summaries will be prepared with respect to two baselines:

- Baseline I: Baseline just prior to randomisation in study 16159A (Baseline 2 in 16159A)
- Baseline II: Baseline in study 16159B.

Unless otherwise specified, baseline will be Baseline II.

Summaries will be prepared overall and by the previous treatment (treatment group in the studies feeding into this extension study or previous treatment for patients not included in any Lu AF35700 study before). In order not to have too many “previous treatments”, these will be grouped into the following categories:

- Lu AF35700
- Risperidone/Olanzapine (16159A patients)
- Quetiapine
- Previous treatment for patients not included in any Lu AF35700 study before

To explore the safety and effectiveness of daily dosing with Lu AF35700, separate displays will be prepared for patients only receiving daily dosing in this study.

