The classification will be done by the biostatistician.

The APTS will be used for presentations of safety data whereas the FAS will be used for presentation of efficacy data. Data listings will be based on the APES unless otherwise specified.

6 Descriptive Statistics

Unless otherwise specified, summary statistics (n, arithmetic mean, standard deviation [SD], median, lower and upper quartiles, minimum and maximum values) will be presented for continuous variables, and counts and, if relevant, percentages will be presented for categorical variables.

Summaries will be prepared overall and by the previous treatment (treatment group in study 16159A). To reflect the grouping of treatments in study 16159A, these will be grouped into the following categories (for 16159A patients only):

- Lu AF35700 10 mg
- Lu AF35700 20mg
- RIS/OLZ

Unless otherwise specified, data listings will include site, previous treatment group, patient screening number (from extension study), and lead-in study-Baseline information on sex, age, race, and weight. For the data listings, the previous treatment will be displayed as the specific treatment received in the lead-in study, i.e. it will belong to one of the categories Lu AF35700 10mg, Lu AF35700 20mg, Lu AF35700 30mg, Risperidone, Olanzapine, or Quetiapine.

7 Patient Disposition

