7.2 Withdrawals

The number of patients who withdrew from treatment will be summarized overall and by previous treatment both by primary reason for withdrawal, and all reasons for withdrawal.

Patients who withdrew from treatment will be listed and the listing will include the reason type (primary or secondary reason for withdrawal from treatment), the reason, specification of other reason, previous treatment group, date of Visit 2, date of withdrawal from treatment, and number of days on IMP in this study. Note that patients can have more than one secondary reason for withdrawal from treatment so the listing will include both the primary reason for withdrawal from treatment and all reasons for withdrawal from treatment.

Kaplan-Meier failure plots of time to withdrawal from treatment will be presented for the total group. The time will be calculated from the date of first dose of IMP in this extension study (for handling of missing IMP start date, see section 19.3.1) to the date of completion or withdrawal from treatment. Patients who completed treatment will be regarded as censored.

All tables and graphs will be based on the APTS. Listings will be based on the APES.

8 Demographics and Baseline Characteristics

Demographics (sex, age, age group, race, and ethnicity); baseline characteristics (height, weight, BMI, and waist circumference); baseline disease characteristics (age – and years since diagnosis of schizophrenia, years since first – and number of antipsychotic treatments, number of psychiatric hospitalizations), social histories; and baseline efficacy variables (PANSS total and subscale scores, CGI-S score, and PSP total score) will be summarized overall and by previous treatment group. CGI-S will be summarized both as a continuous and a categorical variable.

Concurrent as well as relevant past medical, neurological, and psychiatric disorders at the lead-in study Screening Visit will be coded using the *Medical Dictionary for Regulatory Activities* (MedDRA) and summarized.

A concurrent medical, neurological, or psychiatric disorder is a disorder that is ongoing at the Screening Visit of the lead-in study. A past medical, neurological, or psychiatric disorder is a disorder that ended prior to the Screening Visit of the lead-in study.

Demographics and baseline characteristics will be summarized based on the APTS, and baseline efficacy variables will be summarized based on the FAS.

9 Recent and Concomitant Medication

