11.1 General Efficacy Analysis Methodology

Unless otherwise specified, all the efficacy analyses will be based on the FAS.

All the tables and graphs will be presented overall and by previous treatment group unless otherwise specified.

All the confidence intervals (CIs) will be two-sided, 95% CIs.

Descriptive statistics for the absolute scores and the change from baseline scores for the efficacy variables will be presented by study week using all available observations (observed cases [OC] data). The tables will be repeated for LOCF values.

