12.3 Clinical Safety Laboratory Test Data

12.3.1 Data Presentation

The PCS criteria used for the clinical safety laboratory tests are the Lundbeck standard PCS criteria described in SOP_09978: *PV – PCS and standard reference values for laboratory investigations, vital signs and ECGs in clinical studies*, version 6, and are also included in [Table 1](#).

The clinical safety laboratory test values will be presented either in conventional or Système International (SI) units.

Descriptive statistics for the laboratory parameters in the Treatment Period, both absolute values and changes from baseline, will be presented by test and week and the last assessment in the Treatment Period. The summaries for the absolute values will also include summaries for baseline.

The number and percentage of patients with at least one PCS low value or PCS high value at any post-baseline assessment in the Treatment Period will be summarized by laboratory parameter. All available assessments in the period will be included in the evaluation of PCS.

Non-fasting tests of S-Cholesterol, S-Glucose, S-HDL Cholesterol, S-LDL Cholesterol, and S-Triglycerides will be evaluated separately and only for PCS values.

Prolactin will also be presented by detailed previous treatment group, i.e. where the RIS/OLZ group is split into whether the patient received Risperidone or Olanzapine in the lead-in study as well as by sex.

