As mentioned in section 2, due to a higher-than-anticipated roll-over rate and a lower-than-anticipated attrition rate from study 16159A, only patients from study 16159A and 16323A are enrolled in the study and the majority of the patients enrolled are from study 16159A.

The 4 patients enrolled from study 16323A come from different treatment regimens than those from study 16159A. Therefore, data from these 4 patients will only be presented in listings, i.e. they will not contribute to any summary tables.

This also means that the definition of the previous treatment groups included in this document have been changed from what was defined in the study protocol to accurately reflect the treatment received in the lead-in study.

Another implication of this change is that the analysis sets defined in section 5 have been updated to facilitate the analyses as well as to make it possible to include the patients from 16323A in listings.

The clinical study protocol defines the baseline just prior to randomization in study 16159A as an additional baseline and specifies that summary tables will be prepared both with respect to that baseline and the baseline defined in this document. However, these additional summaries will not be created, as it is considered sufficient to evaluate the data captured in this long-term study alone.

The above change also means that the baseline term referring to baseline just prior to randomization in study 16159A is removed from all statistical models.

In the protocol, it is stated that separate displays of descriptive statistics will be prepared for patients only receiving daily dosing in study 16159B. This will not be done, as it is considered sufficient to provide the tables including all patients regardless of dosing regimen.

19 Details on Data Handling

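### The primary laboratory, weight, vital-sign and ECG tables drop the protocol's split by previous treatment, and SAP section 18 does not declare it

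*SAP*

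**What the plan says.** Protocol section 17.3 sets the rule for descriptive summaries: "Summaries will be prepared overall and by the previous treatment (treatment group in the studies feeding into this extension study", with patients new to the drug grouped by their own earlier treatment. SAP section 6 repeats it: "Summaries will be prepared overall and by the previous treatment (treatment group in study 16159A". It names three groups: Lu AF35700 10 mg, Lu AF35700 20 mg, and risperidone/olanzapine combined. Neither sentence exempts safety data.

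SAP section 12.2, which governs laboratory tests, weight/BMI/waist, vital signs and ECG, says: "All the tables and graphs will be presented for the total group". Sections 12.3.1, 12.4 and 12.5 add no split, with one clear exception: "Prolactin will also be presented by detailed previous treatment group". The liver-injury plot in section 12.3.2 is to show patient counts per treatment group, but that term is not defined there.

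Elsewhere the SAP keeps the split. For efficacy, section 11.1 says: "All the tables and graphs will be presented overall and by previous treatment group unless otherwise specified". For demographics and baseline characteristics, including weight, BMI and waist, section 8 says they "will be summarized overall and by previous treatment group. CGI-S will be summarized both as a continuous and a categorical variable". Sections 12.1.6 and 12.1.9 split three adverse-event tables.

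SAP section 18 reports that "the definition of the previous treatment groups included in this document have been changed from what was defined in the study protocol". It also declares that summaries against the pre-randomisation 16159A baseline are dropped, that the four 16323A patients appear in listings only, and, of the protocol's promise that "separate displays of descriptive statistics will be prepared for patients only receiving daily dosing in study 16159B. This will not be done", gives a reason. It does not mention removing the previous-treatment split from the safety tables.

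**The concern.** The affected variables are primary endpoints (Protocol section 16.1, SAP section 4.1), and Protocol section 3.2 singles out metabolic change as an important long-term risk. Under SAP section 3.1, baseline for 16159A patients is that study's Primary Outcome Visit, when they were still on their randomised lead-in treatment. A change from baseline therefore means different things in different patients. For some it is change on continued Lu AF35700. For others it is change after leaving risperidone or olanzapine. Under Protocol section 6.1 everyone starts at 10 mg/day, so patients who had been on 20 mg also change regimen at entry.

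The same holds for PCS criteria defined relative to baseline in SAP Appendix III, such as a weight change of at least 7% or a QTcF increase above 60 ms. As planned, a reader gets baseline weight by group but not weight change by group, and the exploratory efficacy results are separated while the primary safety results are not.

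A smaller, separate matter concerns the laboratory PCS percentages. They count any post-baseline PCS value against absolute or reference-range limits and do not set apart patients who were already PCS at baseline.

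**Working it through.** **Side-by-side reading.** The plan states no figure on this point to reproduce; Protocol section 17.11 and SAP section 16 say no formal sample size calculation was done.

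| Place | Split by previous treatment? |
|---|---|
| Protocol 17.3 | Yes, no safety exception |
| SAP 6 | Yes, three named groups |
| SAP 8, baseline weight/BMI/waist | Yes |
| SAP 11.1, exploratory efficacy | Yes |
| SAP 12.1, adverse events | Three tables (two in 12.1.6, one in 12.1.9) |
| SAP 12.2–12.5, labs, weight, vital signs, ECG | No; prolactin excepted, liver plot unclear |
| SAP 18 | Removal not declared |

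The qualifiers that open Protocol 17.3 and SAP 6 attach to which statistics are shown, not to the previous-treatment sentence.

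**Illustration 1: weight gain of at least 7%.** Assumed: normally distributed percentage change, SD 5–8%, mean 0% in continuing patients. P(change ≥ 7%) = 1 − Φ((7 − mean)/SD).

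| Mean change | SD 5% | SD 8% | Gap from mean 0 (points) |
|---|---|---|---|
| 0% | 8.1% | 19.1% | 0 |
| −2% | 3.6% | 13.0% | −4.5 / −6.0 |
| +2% | 15.9% | 26.6% | +7.8 / +7.5 |

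Mean changes can also cancel. With an assumed 25% share of switchers, +0.5 kg in continuers and −1.5 kg in switchers pool to 0.75 × 0.5 − 0.25 × 1.5 = 0.0 kg.

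**Illustration 2: precision of split tables.** SAP section 16 gives more than 500 patients; 500 is used. Group sizes and a 10% event rate are assumed.
- One group: half-width 1.96 × √(0.09/n) = 3.7 points at n = 250 and 5.9 at n = 100.
- Difference between two groups: 1.96 × √(0.09 × (1/a + 1/b)) = 5.3 points for 250/250, 5.6 for 333/167 and 6.6 for 400/100.
- 10 mg against 20 mg: 6.4 points with 167 each and 7.4 with 125 each.

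**Illustration 3: PCS already present at baseline.** Printed percentage = bq + (1 − b)i, and share already present = bq / printed. Assumed: b (PCS at baseline) 5%, 10%, 20%; q (persisting) 50%, 80%; i (new onset) 2%, 5%, 10%.
- Lowest printed: 0.05 × 0.5 + 0.95 × 0.02 = 4.4%. Highest: 0.20 × 0.8 + 0.80 × 0.10 = 24.0%.
- Share already present at baseline: 57–91% at 2% new onset, 34–80% at 5%, and 21–67% at 10%.

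The printed percentage alone does not fix that share. The point applies to laboratory tests with no matching entry limit, such as fasting lipids, prolactin and creatine kinase. It also applies to known diabetics with HbA1c from 6.5% to below 7.0%: the entry criterion for 16159A patients admits them, while the PCS limit is 6.5%.

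**The case against.** The best defence is that section 12 is deliberate drafting. SAP section 6 is general; sections 12.1.1 and 12.2 are specific, default to the total group and name exceptions. The study is single-arm and open-label, its primary objective is the overall long-term safety of Lu AF35700, and no between-group safety inference is planned. Protocol section 17.9.2 asks only that these data be summarised. This may excuse the SAP internally, but it does not remove the departure from Protocol section 17.3 or explain the silence of SAP section 18, which declares comparable dropped displays.

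The safeguards are real. Listings carry previous treatment and show all values for patients with a post-baseline PCS value. Protocol sections 9.5.2 to 9.5.5 require clinically significant laboratory, vital-sign, weight/waist and ECG abnormalities to be recorded as adverse events, and treatment-emergent events by preferred term are shown by previous treatment. Individual cases are traceable and investigator-judged abnormalities get by-group rates. By-group mean changes and PCS rates with denominators are still missing.

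Other points limit the claim without overturning it. Most adverse-event tables and the C-SSRS and movement-scale summaries are also total-only, so the gap is wider than sections 12.2–12.5. The case for separating 10 mg from 20 mg is weaker than for separating switchers: 20 mg is possible again from Week 1, while weight, laboratory tests and ECG are first measured after baseline at Week 4. Most of the illustrated gaps are close to the precision limits. The exclusion for laboratory values judged a risk may lower baseline PCS prevalence, so the 5–20% used above could be too high.

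**Conclusion.** The concern holds. Protocol section 17.3 promises a by-previous-treatment display that SAP section 12.2 removes from primary safety endpoints, prolactin apart and possibly the liver plot, and SAP section 18 does not record the change. It should be corrected. It affects what the summary tables can show, not the data collected.

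The numerical effect is unknown because the documents give no group sizes, variability or PCS rates. It is zero if switchers and continuers change alike; on the assumed weight values it is 4.5 to 7.8 points in the by-group rate, in either direction. At the assumed group sizes the split would be descriptive, and only larger gaps would stand out. Separating baseline PCS status is an optional improvement, not a breach: the protocol asks only that PCS values be flagged and summarised.

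**What to change.** **Main change.** In SAP sections 12.2 to 12.5, replace the total-group rule for change and PCS tables with presentation by previous treatment (Lu AF35700 10 mg, Lu AF35700 20 mg, risperidone/olanzapine) and in total. Define treatment group in section 12.3.2 the same way. If total-only display is kept for any of these tables, declare and justify it in section 18. That entry should also cover the adverse-event, C-SSRS and movement-scale summaries that stay total-only.

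**Optional addition.** For laboratory tests with absolute PCS limits and no matching entry limit, add the number and percentage with a post-baseline PCS value among patients not PCS at baseline, or a shift table of baseline against worst post-baseline status.

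**Cost.** SAP wording and programming on data already held; no new data collection. The output becomes longer and the by-group cells smaller.

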12.3 Clinical Safety Laboratory Test Data

12.3.1 Data Presentation

The PCS criteria used for the clinical safety laboratory tests are the Lundbeck standard PCS criteria described in SOP_09978: *PV – PCS and standard reference values for laboratory investigations, vital signs and ECGs in clinical studies*, version 6, and are also included in [Table 1](#).

The clinical safety laboratory test values will be presented either in conventional or Système International (SI) units.

Descriptive statistics for the laboratory parameters in the Treatment Period, both absolute values and changes from baseline, will be presented by test and week and the last assessment in the Treatment Period. The summaries for the absolute values will also include summaries for baseline.

The number and percentage of patients with at least one PCS low value or PCS high value at any post-baseline assessment in the Treatment Period will be summarized by laboratory parameter. All available assessments in the period will be included in the evaluation of PCS.

Non-fasting tests of S-Cholesterol, S-Glucose, S-HDL Cholesterol, S-LDL Cholesterol, and S-Triglycerides will be evaluated separately and only for PCS values.

Prolactin will also be presented by detailed previous treatment group, i.e. where the RIS/OLZ group is split into whether the patient received Risperidone or Olanzapine in the lead-in study as well as by sex.

